13.8 Reporting and Exclusions

13.8.1 Evaluation of Toxicity

All participants who have received at least one dose of nivolumab and ipilimumab will be evaluable for toxicity from the time of their first treatment.

13.8.2 Evaluation of the Primary Efficacy Endpoint

To be included in the assessment of the primary objective, patients need to receive at least one cycle.

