5. TREATMENT PLAN

5.1 Treatment Regimen by histology:

For melanoma: patients will be treated with the combination regimen of nivolumab 1 mg/kg combined with ipilimumab 3mg/kg Q3W (4 doses), followed by nivolumab monotherapy (480 mg Q4W) until progression or unacceptable toxicity.

For nonsmall cell lung cancer and head and neck cancer: patients will be treated with nivolumab 3mg/kg Q2W + ipilimumab 1mg/kg Q6W

For small cell lung cancer, breast cancer, and bladder cancer: patients will be treated with nivolumab 1mg/kg + ipilimumab 3mg/kg Q3W x 4 doses, followed by nivolumab 240 mg Q2W

For renal cell carcinoma and other solid tumors (not listed above): patients will be treated with nivolumab 3mg/kg + ipilimumab 1mg/kg Q3W x 4 doses, followed by nivolumab 480 mg Q4W

Each treatment cycle will be 6 weeks, with the exception of the nivolumab maintenance monotherapy phase in melanoma, renal cell carcinoma and other solid tumors, when each cycle will be 8 weeks. Treatment will be administered on an outpatient basis. Reported adverse events and potential risks are described in Section 7. Appropriate dose modifications are described in Section 6. No investigational or commercial agents or therapies other than those described below may be administered with the intent to treat the participant's malignancy.

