11.1.6 Progression-Free Survival

Overall Survival: Overall Survival (OS) is defined as the time from registration to death due to any cause, or censored at date last known alive.

Progression-Free Survival: Progression-Free Survival (PFS) is defined as the time from registration to the earlier of progression or death due to any cause. Participants alive without disease progression are censored at date of last disease evaluation.

Time to Progression: Time to Progression (TTP) is defined as the time from randomization (or registration) to progression, or censored at date of last disease evaluation for those without progression reported.

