13.2 Sample Size, Accrual Rate and Study Duration

Accrual of up to 20 patients may be required to achieve 18 evaluable patients.

The primary endpoint is the rate of overall survival at 3 months (OS3). Any patient whose vital status at 3 months cannot be determined will be counted as having died. A Simon two-stage design will be used to compare a null hypothesis OS3 of 18% against an alternative of 43%. Nine patients will be enrolled in the first stage. If 0 or 1 patients are alive at 3 months, the trial will be stopped early. If 2 or more patients are alive at 3 months, we will enroll an additional 9 patients. If at least 6 patients among the total of 18 patients are alive at 3 months, then the treatment would be promising in the cohort. This design has a type-I error of 8% (target 10%) and power of 86% (target 85%). If the null hypothesis is true, then the probability is 0.50 of stopping at the end of the first stage.

In addition, we will assess for the primary outcome of any histologic, molecular subtype (e.g., ER/PR-positive, HER2-positive breast cancer, EGFR mutant lung cancer) with 6 patients

enrolled for that particular subtype. If no patient within a particular histologic subtype has achieved the primary outcome, then patients with that histology will no longer be eligible to enroll in the trial. Under the alternative hypothesis (i.e., OS3 = 43%), the probability is 0.03 of observing no patients with OS3 among 6 patients.

The accrual rate is based on our institutional patient volume of 3-4 patients per month with leptomeningeal carcinomatosis seen in our multidisciplinary brain metastasis clinic. We estimate that 1-2 patients per month will be eligible for this protocol. Therefore, 20 patients will be accrued within 10-20 months. Based on six months of follow-up (median survival of patients is approximately 2-4 months), total study duration will be 24 months.

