13.5 Analysis of Primary Endpoints

The primary endpoint is the rate of overall survival at 3 months (OS3). Any patient whose vital status is unknown due to loss of follow-up will be classified as having died for purposes of estimating the primary endpoint. The proportion of patients alive at 3 months will be summarized with a 90% confidence interval estimated using the method of Atkinson and Brown, which allows for the two-stage design. Based on a sample of 18 patients, the confidence interval will be no wider than 0.42.

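### Section 13.8.2 does not define receiving one cycle for the primary OS3 analysis; on a stricter reading than starting it, known cycle-1 deaths can leave the denominator and be replaced

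*Combined protocol and SAP*

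**What the plan says.** The primary endpoint is the proportion alive at 3 months, tested in a Simon two-stage design with a null of 18% and an alternative of 43% (13.2). The passages that settle who counts are these:

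- **13.8.2, primary endpoint:** "To be included in the assessment of the primary objective, patients need to receive at least one cycle".
- **13.8.1, toxicity, immediately before it:** "All participants who have received at least one dose of nivolumab and ipilimumab will be evaluable for toxicity".
- **5.1:** "Each treatment cycle will be 6 weeks", with 8-week cycles only in some maintenance phases.
- **11.1.6:** "Overall Survival (OS) is defined as the time from registration to death due to any cause".
- **13.2:** "Accrual of up to 20 patients may be required to achieve 18 evaluable patients". Also "Nine patients will be enrolled in the first stage", stopping if 0 or 1 is alive at 3 months. The final rule calls the treatment promising on this condition: "If at least 6 patients among the total of 18 patients are alive at 3 months".
- **13.5:** "Any patient whose vital status is unknown due to loss of follow-up will be classified as having died". Section 13.2 has the same rule for vital status at 3 months.
- **4.1:** a registration with no protocol therapy afterwards is cancelled.
- **3.1.4:** life expectancy need only exceed 3 weeks.

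No passage says what receiving a cycle requires, and none says that a known death during cycle 1 stays in the denominator as a failure.

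**The concern.** Survival is counted from registration, but entry to the only primary analysis depends on something that happens later. Entry requires a life expectancy of only half a cycle or so, and sections 2.1 and 2.3 put untreated median survival at 4 to 6 weeks, about one cycle. If patients must get through cycle 1 to be counted, the analysis can drop the patients who did worst and enrol others in their place. A documented early death would then be treated more leniently than a loss to follow-up, which counts as a failure.

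The success bound is 6 of 18, so one patient can decide the result. Suppose two of the first 18 treated patients die in week 3 and are replaced, stage 1 is passed, and 6 of the 18 remaining are alive at 3 months. The result is promising. If one of those six is a replacement, the first 18 treated have only 5 alive and the result is not promising. This is a single-arm trial, so the choice of reading could be made after the outcomes are known.

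**Working it through.** **Which reading.** Three are possible: starting cycle 1, receiving all its doses, or completing the 6 weeks.

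- Starting would add little to 4.1, which already cancels untreated registrations.
- 13.8.1 uses a one-dose test and 13.8.2 uses different words.
- 11.2.1 applies the same one-cycle test to CNS response, then adds a note keeping patients who progress before the end of cycle 1 evaluable. Such a note is mainly needed if the test would otherwise remove patients who did not finish the cycle. 13.8.2 has no such note.

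This favours the stricter reading. It is not proof, because 11.2.1 also requires re-evaluation and its note may serve that condition.

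**Reproducing the design (13.2).** With p = 0.18, P(stop after stage 1) = P(Bin(9, 0.18) ≤ 1) = 0.1676 + 0.3312 = 0.499, as stated (0.50). Type-I error is the sum over x = 2 to 9 of P(Bin(9, 0.18) = x) × P(Bin(9, 0.18) ≥ 6 − x):

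0.2908×0.0615 + 0.1489×0.2105 + 0.0490×0.5012 + 0.0108×0.8324 + 0.0017 = 0.0845, which is the stated 8%.

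This holds when all 18 patients count and each has an 18% chance of being alive at 3 months.

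**Effect of exclusion.** The documents give no rates, so two quantities are assumed: e, the share of patients excluded as early deaths, and q, the share of 3-month survivors excluded because they stopped in cycle 1. Under the null, each enrolled patient is

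- an included survivor with probability 0.18(1 − q),
- excluded with probability e + 0.18q,
- an included failure with probability 0.82 − e.

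The expected OS3 among included patients is 0.18(1 − q)/(1 − e − 0.18q). With q = 0 and e = 10%, this is 0.18/0.90 = 0.20. With e = 5% or 20% it is 0.189 or 0.225. The two effects cancel in the estimate at q = e/0.82, that is 6%, 12% or 24% for e = 5%, 10% or 20%.

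Type-I error comes from exact enumeration: stop if at most 1 included survivor is seen in stage 1; otherwise enrol until 18 are evaluable or 20 are enrolled; succeed with at least 6 included survivors. The bound of 6 is also applied if fewer than 18 are evaluable at 20, an assumption because the plan gives no rule for that case.

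| Stage 1 counted as | q | e = 5% | e = 10% | e = 20% | Ceiling |
|---|---|---|---|---|---|
| Nine enrolled (as 13.2 says) | 0 | 0.099 | 0.110 | 0.121 | 0.123 |
| Nine enrolled | 5% | 0.083 | 0.092 | 0.100 | 0.102 |
| Nine enrolled | 10% | 0.069 | 0.075 | 0.081 | 0.083 |
| Nine evaluable | 0 | 0.101 | 0.115 | 0.129 | 0.136 |

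The ceilings exist because at most two patients can be added. For q = 0 with nine enrolled, the limit is the sum over x = 2 to 9 of P(Bin(9, 0.18) = x) × P(Bin(11, 0.18) ≥ 6 − x) = 0.1234. With nine evaluable it is P(Bin(20, 0.18) ≥ 6) = 0.1356. With nine enrolled and q = 0, the 10% target is first passed at e of about 5.3%.

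**Reaching 18 evaluable.** With q = 0, the probability that at least 18 of 20 are evaluable is 0.92, 0.68 or 0.21 for e = 5%, 10% or 20%.

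**The case against.** The strongest reply is that the harm rests on one contested reading. If receiving a cycle means starting it, the rule is close to all treated patients and there is essentially no bias. A budget of two extra patients also sits badly with excluding everyone who does not complete six weeks of a disease this aggressive. Sections 13.2 and 13.5 state the endpoint and decision rule without any cycle condition. This stands as a reason not to treat the stricter reading as settled. It does not defend the text, which leaves the choice open.

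The second reply is that the effect is small. The sponsor's criterion is the 10% target, and 8% is only what the discrete design attains. With nine enrolled, the most that can be added above the target is 0.123 − 0.100, about 2.3 points. Excluding early stoppers who survive works the other way: at q = 5% the error is at or close to the target, and at q = 10% it stays below the designed 0.0845. A move from 18% to 20% is also minor beside a 90% interval that 13.5 allows to be 0.42 wide. All of this stands. Section 2.2.3 reports 22.0% to 24.5% of patients stopping the combination for treatment-related events, so early stopping is plausible. That figure comes from a melanoma study and covers all treatment, so it does not fix q for cycle 1 here.

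A reader might infer that the plan is in effect a six-week landmark analysis, with a null OS3 far above 18%. The documents do not support that: they neither require completion of the cycle nor give a survival curve from which to calculate it.

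**Conclusion.** The defect is real: the plan does not settle who counts in its only primary analysis, and no other passage repairs this. The consequence is conditional. It needs a reading stricter than starting cycle 1, some early deaths, and few surviving early stoppers among the excluded. Under those conditions OS3 tends to read too high (18% becomes 20% with 10% excluded as early deaths), and type-I error can pass the 10% target by up to about 2.3 points with nine enrolled in stage 1, or 3.6 points with nine evaluable. These figures also assume the bound stays at 6 alive when fewer than 18 are evaluable.

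It would go too far to infer that OS3 will be inflated or that error control is lost. Depending on who is excluded, the error can lie above or below the stated 8%. What can be said is that 8% is not assured, and that near the 6-of-18 bound the choice of reading could change the conclusion.

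**What to change.** In 13.8.2, replace the one-cycle condition with wording such as:

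> All registered patients who receive any dose of nivolumab or ipilimumab are included in the primary analysis, with survival measured from registration. Death by 3 months, or unknown vital status at 3 months, is a failure.

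In 13.2, define evaluable the same way, so that the first 9 and the first 18 treated patients drive the two decisions. Replace only registrations cancelled before any dose under 4.1. Deaths between registration and first dose would still be left out, so report how many cancellations were due to death. If a one-cycle set is wanted, define what receiving the cycle requires and keep it as a labelled supportive analysis only.

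The cost is small text edits, one reported count and one supportive analysis, with no extra patients or procedures. The observed OS3 may be less favourable.

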APPENDIX A

PERFORMANCE STATUS CRITERIA

ECOG Performance Status Scale		Karnofsky Performance Scale	
Grade	Descriptions	Percent	Description
0	Normal activity. Fully active, able to carry on all pre-disease performance without restriction.	100	Normal, no complaints, no evidence of disease.
		90	Able to carry on normal activity; minor signs or symptoms of disease.
1	Symptoms, but ambulatory. Restricted in physically strenuous activity, but ambulatory and able to carry out work of a light or sedentary nature (e.g., light housework, office work).	80	Normal activity with effort; some signs or symptoms of disease.
		70	Cares for self, unable to carry on normal activity or to do active work.
2	In bed <50% of the time. Ambulatory and capable of all self-care, but unable to carry out any work activities. Up and about more than 50% of waking hours.	60	Requires occasional assistance, but is able to care for most of his/her needs.
		50	Requires considerable assistance and frequent medical care.
3	In bed >50% of the time. Capable of only limited self-care, confined to bed or chair more than 50% of waking hours.	40	Disabled, requires special care and assistance.
		30	Severely disabled, hospitalization indicated. Death not imminent.
4	100% bedridden. Completely disabled. Cannot carry on any self-care. Totally confined to bed or chair.	20	Very sick, hospitalization indicated. Death not imminent.
		10	Moribund, fatal processes progressing rapidly.
5	Dead.	0	Dead.

APPENDIX B

TUMOR ASSESSMENT PER IMMUNE-RELATED RESPONSE CRITERIA

Immune-related Response Criteria (irRC) are derived from modified World Health Organization (mWHO) conventions. Assessments of lymph nodes are derived from current RECIST guidelines.

Definitions of Measurable/non-Measurable Lesions

All measurable and non-measurable lesions should be assessed at Screening and at the defined tumor assessment time points. Additional assessments may be performed, as clinically indicated for suspicion of progression.

Measurable Lesions

Measurable lesions are lesions that can be accurately measured in 2 perpendicular diameters, with at least 1 diameter ≥ 20 mm and the other dimension ≥ 10 mm (10 mm x 10 mm for spiral CT with cuts of 5 mm). The area will be defined as the product of the largest diameter with its perpendicular.

Lymph nodes may also be considered measurable. To be considered pathologically enlarged and measurable, a lymph node must be at least 15 mm in short axis when assessed by CT scan (CT scan slice thickness recommended to be no greater than 5 mm).

Non-Measurable Lesions

Non-measurable (evaluable) lesions are all other lesions, including unidimensional measurable disease and small lesions (lesions without at least 1 diameter ≥ 20 mm, or pathological lymph nodes with short axis $\square 15$ mm), and any of the following: lesions occurring in a previously irradiated area (unless they are documented as new lesions since the completion of radiation therapy), bone lesions, leptomeningeal disease, ascites, pleural or pericardial effusion, lymphangitis cutis/pulmonis, abdominal masses that are not pathologically/cytologically confirmed and followed by imaging techniques and cystic lesions. Lymph nodes that have a short axis < 10 mm are considered non-pathological and should not be recorded or followed.

Definitions of Index/non-Index Lesions

Index Lesions

Measurable lesions, up to a maximum of 5 lesions per organ and ten lesions in total, must be identified as index lesions to be measured at Screening. The index lesions should be representative of all involved organs. In addition, index lesions must be selected based on their size (eg, lesions with the longest diameters), their suitability for accurate repeat assessment by imaging techniques, and how representative they are of the subject's tumor burden. At Screening, a Sum of the Product Diameters (SPD) for all index lesions will be calculated and considered the baseline SPD. The baseline sum will be used as the reference point to determine the objective tumor response of the index lesions at tumor assessment.

Non Index Lesions

Measurable lesions, other than index lesions, and all sites of non-measurable disease, will be identified as non-index lesions. Non-index lesions will be evaluated at the same assessment time

points as the index lesions. In subsequent assessments, changes in non-index lesions will contribute only in the assessment of complete response.

Calculation of Sum of Product of Diameters (SPD)

Sum of Product of Diameters is an estimate of tumor burden. The 2 greatest perpendicular diameters are used to estimate the size of each tumor lesion. The SPD is calculated as the sum of the product of the diameters for index tumor lesions. Several variations of the SPD are identified for the purpose of classification of tumor responses.

SPD at Baseline: The sum of the product of the diameters for all index lesions identified at baseline prior to treatment on Day 1.

SPD at tumor assessment: For every on-study tumor assessment collected per protocol or as clinically indicated, the SPD at tumor assessment will be calculated using tumor imaging scans. All index lesions and all new measurable lesions that have emerged after baseline will contribute to the SPD at tumor assessment (irSPD).

SPD at NADIR: For tumors that are assessed more than 1 time after baseline, the lowest value of the SPD (SPD Baseline or SPD at tumor assessment) is used to classify subsequent tumor assessments for each subject. The SPD at tumor assessment using the irRC for progressive disease incorporates the contribution of new measurable lesions. Each net percentage change in tumor burden per assessment using irRC accounts for the size and growth kinetics of both old and new lesions as they appear. In this study the irRC as defined by the Investigator will serve as the basis of key endpoints for efficacy analyses and guide clinical care.

Definition of Index Lesion Response

Immune-related Complete Response (irCR), which is defined as complete disappearance of all index lesions. Lymph nodes that shrink to < 10 mm short axis are considered normal.

Immune-related Partial Response (irPR), which is defined as a decrease, relative to baseline, of 50% or greater in the sum of the products of the 2 largest perpendicular diameters of all index and all new measurable lesions (ie, Percentage Change in Tumor Burden), in the absence of irCR.

Note: the appearance of new measurable lesions is factored into the overall tumor burden, but does not automatically qualify as progressive disease until the SPD increases by $\geq 25\%$ when compared to SPD at nadir

Immune-related Stable Disease (irSD), which is defined as not meeting the criteria for irCR or irPR, in the absence of immune-related progressive disease (irPD)

Immune-related Progressive Disease (irPD), which is defined as at least a 25% increase in Tumor Burden (ie, taking sum of the products of all index lesions and any new measurable lesions) when compared to SPD at nadir.

Definition of Non-Index Lesion Response

Immune-related Complete Response (irCR), which is defined as complete disappearance of all non-index lesions. Lymph nodes that shrink to < 10 mm short axis are considered normal.

Immune-related Partial Response (irPR), non-index lesion(s) are not considered in the definition of PR, this term does not apply.

Immune-related Stable Disease (irSD), non-index lesion(s) are not considered in the definition of SD, this term does not apply.

Immune-related Progressive Disease (irPD), increases in number or size of non-index lesion(s) does not constitute progressive disease unless/until Tumor Burden increases by 25% (ie, the SPD at nadir of index lesions and any new measurable lesions increases by the required amount).

Impact of New Lesions on irRC

New lesions alone do not qualify as progressive disease. However their contribution to total tumor burden is included in the SPD which in turn feeds into the irRC for tumor response. Therefore, new non-measurable lesions will not discontinue any subject from the study.

Definition of Overall Response Using irRC Will Be Based on the Following Criteria:

[figure not shown]
- Immune-related Complete Response (irCR): Complete disappearance of all tumor lesions (index and non-index), together with no new measurable or unmeasurable lesions, for at least 4 weeks from the date of documentation of irCR. All lymph nodes short axes must be < 10 mm.
- Immune-related Partial Response (irPR): The sum of the products of the 2 largest perpendicular diameters of all index lesions is measured and captured as the SPD baseline. At each subsequent tumor assessment, the sum of the products of the 2 largest perpendicular diameters of all index lesions and of new measurable lesions are added together to provide the Immune Response Sum of the Product of the Diameters (irSPD). A decrease, relative to baseline of the irSPD of 50% or greater is considered an irPR, in the absence of irCR. Must be confirmed no less than 4 weeks from the first irPR.
- Immune-related Stable Disease (irSD): irSD is defined as the failure to meet criteria for immune complete response or immune partial response, in the absence of progressive disease.
- Immune-related Progressive Disease (irPD): It is recommended in difficult cases (eg, increase in SPD or irSPD accompanied with significant individual lesion regression, “mixed response”, or in presence of stable or improving performance status/clinical condition) to confirm PD at the following tumor assessment. Any of the following will constitute progressive disease:
 - At least 25% increase in the SPD of all index lesions over nadir SPD calculated for these lesions
 - At least a 25% increase in the SPD of all index lesions and new measurable lesions
 - (irSPD) over the nadir SPD calculated for the index lesions.

PROTOCOL NUMBER:
NCI: TBD
BMS:CA209-405

TITLE: Phase II Trial of Ipilimumab and Nivolumab in Leptomeningeal Metastases from Melanoma

